Targeted Health Coaching Intervention to Improve Physical Activity Maintenance and Mobility Post-
Structured Cardiac Rehabilitation Programming Among Older Adults: A Pilot Study

Document Date: 2/23/2024

NCT05773287

Purpose of the Study

To identify factors and triggers influencing physical activity (PA) participation after structured cardiac rehabilitation (CR) among older adults who have enrolled in a center-based CR program, and compare the effects of a targeted health coaching intervention versus standard care immediately following structured CR on PA maintenance and functional fitness.

Background & Significance

Approximately 800,000 individuals in the United States have a heart attack every year, with almost 1 in 4 of those individuals already having suffered a previous heart attack. Attending cardiac rehabilitation (CR) following a cardiovascular event improves cardiorespiratory fitness and health-related quality of life, as well as decreases the risk of future illness and death from heart disease. Unfortunately, once an individual finishes a CR program, continued participation in physical activity (PA) too often reverts to previous sedentary patterns, limiting beneficial health effects. Continued participation in PA post-CR is especially challenging among older adults – likely due to a lack of self-efficacy and confidence in their ability to perform PA due to either their age or other health conditions that make PA more challenging. However, the need to address other health conditions, in conjunction with the benefits of improved strength and mobility, makes continued PA participation following a structured CR program even more useful for older adults. Although individuals typically understand habitual participation in PA is good for their health, we poorly understand why some individuals successfully adhere to and maintain PA habits, while others succumb to barriers preventing them from maintaining the health benefits beyond CR. In addition to understanding factors and triggers influencing PA maintenance beyond CR, little research has developed or investigated interventions targeting this important transition period following structured CR programming to promote continued PA participation “at home”. Therefore, this proposal aims to 1) identify factors and triggers influencing PA participation after a traditional 36-session CR program (Stage 0); and 2) test a targeted health coaching intervention using these identified triggers to optimize PA maintenance and mobility among older adults who completed a center-based CR program.

Design & Procedures

Target-CR will enroll up to 30 adults for this pilot study to identify 26 individuals eligible for participation. The following aims will maximize the value of the data:

Aim 1. To identify factors and triggers influencing PA participation after structured CR among older adults who have enrolled in a center-based CR program.

Aim 2. To compare the effects of a targeted health coaching intervention versus standard care immediately following CR on PA maintenance and functional fitness.

Study Procedures

Study visits are divided into five phases as detailed below.

Phase 1 – Screening/Consent: The Screening/Consent Phase will be completed virtually or in-person in 1-2 visits depending on scheduling and will take a total of about 1 to 2 hours. During this phase, the participant will be asked to do the following:

- Discuss details of the study with study staff and review/sign the consent form
- Provide contact information
- Review medical history
- Complete Mental Health Screening Questionnaire

Phase 2 – Initial Testing: The Initial Testing Phase involves one in-person visit and will take a total of about 2.5 hours. During this phase, the participant will be asked to do the following:

Qualitative Interview – Participants will complete a qualitative interview assessing factors and triggers influencing current physical activity participation. These sessions will be recorded as audio files for future reference by study staff.

- Measure height and weight
- Review medications
- Complete Paffenbarger Physical Activity Questionnaire
- Senior Fitness Test – Participants will perform a chair stand test, arm curl test, chair sit and reach test, back scratch test, 8-foot up and go test, and step-in-place test.
- Dispense Garmin activity monitor

Phase 3 – Randomization: Upon completion of the Screening/Consent and Initial Testing phases, participants will be randomized to one of two groups:

- Targeted Health Coaching (THC) Group – ~50% of study participants will be in the THC group.
- Standard Care (SC) Group – ~50% of study participants will be in the SC group.

Phase 4 – Intervention: The Intervention Phase will last about 3 months and will be different for the THC and SC groups:

- THC Group – Participants in the THC group will receive an exercise prescription (steps/day) based on their last cardiac rehabilitation session exercise prescription. Participants will be provided a Garmin wearable device to track steps/day. Additionally, participants will partake in 6 virtual or in-person health coaching sessions lasting approximately 30-60 minutes in duration. These sessions will take place approximately every other week during the 3-month intervention period.
- SC Group – Participants in the SC group will receive an exercise prescription (steps/day) based on their last cardiac rehabilitation session exercise prescription. Participants will be provided a Garmin wearable device to track steps/day. Additionally, participants will be provided with a single virtual or in-person education session, lasting approximately 30 minutes, at the beginning of the 3-month intervention period.

Phase 5 – Recurrent Questionnaire Testing: The Recurrent Questionnaire Testing Phase will occur throughout the duration of the 3-month intervention period. The questionnaire will be used to gather information on factors and triggers influencing PA maintenance. The questionnaire will be administered remotely or in-person based on participant preference at weeks four, eight, and twelve during the 3-

month intervention period. The questionnaire will be available in paper form or online and will take approximately 10 to 15 minutes each time it is completed.

Phase 6 – Follow-up Testing: Follow-up testing includes the same tests completed during the initial testing phase, excluding the qualitative interview. The repeated tests will be completed in one in-person visit that will take a total of 1 to 2 hours.

Selection of Subjects

Inclusion Criteria:

- Willingness to provide informed consent to participate in the Target-CR Study
- Must be able to read and speak English well enough to provide informed consent and understand instructions
- Age \geq 60 years
- Diagnosed with coronary heart disease
- Of adequate clinical stability to allow study participation
- Own a smartphone device for application download

Exclusion Criteria:

- Planned relocation during the 5-month study period
- Medical procedure scheduled within the 5-month study period that may limit physical activity (i.e., joint replacement)
- Decompensated heart failure
- Heart failure – New York Heart Association class IV
- Severe pulmonary hypertension
- End-stage renal disease
- Cardiac transplantation
- Impairment from stroke, injury, or other medical condition that would prevent participation in the intervention
- Dementia that would prevent participation in the intervention and following study protocols
- Any other illnesses that, in the opinion of the local clinician, would negatively impact or mitigate participation in and completion of the protocol
- Psychiatric illness (self-report and screening)
- Hospitalization for any psychiatric condition within one year (self-report)
- Integrative Health Coaching Mental Health Screening Questionnaire score >4 (screening), if not currently in treatment
- Participation in an inpatient substance abuse rehabilitation program within one year
- Exclusion criteria will primarily be identified by way of a phone screen process conducted by a designated member of the study team; however, medical record review may be used to confirm the presence/absence of certain medical conditions listed as inclusion/exclusion criteria.

Subject Recruitment and Compensation

Potential subjects for this study will be recruited from the Duke Cardiopulmonary Rehabilitation clinic at Croasdaile. Potential participants will initially be identified by study staff and cardiac rehab staff familiar with the study. The study may be introduced to the potential participant during the course of their cardiac rehabilitation program or they may be contacted by phone, email or snail mail after they have completed their cardiac rehab program.

The PI will coordinate with the Clinical Operations Supervisor and Manager of the Cardiopulmonary Rehabilitation clinic to identify patients approaching the completion of their cardiac rehabilitation program who may be interested in the research study. If the individual meets most of the inclusion/exclusion criteria, the subject will be invited to attend a private study information session conducted by the PI or designated member of the study team to learn the details of the study. We will allow up to 60 minutes for the subjects to read the consent, ask questions and decide whether or not they are willing to participate in the study.

Participants will receive compensation for completing each scheduled study visit for a maximum of \$150. In addition, participants will keep the wearable device (\$165/device) they were provided for the intervention.

Data Analysis & Statistical Considerations

The Target-CR study will collect both qualitative and quantitative data, utilizing demographic, behavioral/psychosocial, activity, and functional fitness measurements. This is a pilot intervention trial, thus the number of subjects randomized will be ~26 across the 1-year funding period with a target of 13 participants in each group. Given this is a pilot grant, this data will be utilized for future study development of effect sizes and power.

Data from Aim 1 will be utilized in two ways:

- To inform the health coach what the current barriers and triggers influencing the participant's ability to perform physical activity after structured CR. This will be discussed with the participants randomized to the THC group in their initial health coaching session.
- Develop the common themes of factors and triggers reported in this population. We will conduct a thematic analysis utilizing the baseline qualitative interview transcripts and two personnel. The personnel assigned for thematic interpretation will follow a step-by-step process: 1) familiarization with the transcript data; 2) develop an initial set of codes representing observed data meanings and patterns; 3) collate data excerpts by code; 4) group codes into potential themes; 5) review and revise themes with co-transcribing personnel. From this, we will assess the most common baseline self-reported factors and triggers influencing PA participation. Analyses will be focused on descriptive data including frequencies of the common themes identified.

For Aim 2, our statistical approach will be as follows:

We will classify maintenance in two ways – 1) using mean steps/day over the 3-month intervention period; and 2) calculated as (steps/day completed) divided by (steps/day prescribed) times 100 and average this metric over the 3-month study period. Data will be analyzed using Intent-to-Treat and statistical significance will be set at 0.05. We will assess the following:

Primary outcome: Within-group differences in maintenance metrics and Senior Fitness test scores (THC group n=13 vs. SC group n=13). Using 80% power at alpha level 0.05, we should be able to detect an effect size around 0.62 for analyses of pre-to-post change scores using steps per day as the primary outcome using paired t-tests, paralleling published findings.

Secondary outcome: Between-group differences in maintenance metrics and Senior Fitness Test scores (13 vs. 13)

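### The plan makes no allowance for loss after randomisation, and the stated 80% power at an effect of about 0.62 is not reached within an arm even with all 13 retained

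*Combined protocol and SAP*

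**What the plan says.** Under Design & Procedures the plan sets the enrolment cap and its purpose: "Target-CR will enroll up to 30 adults for this pilot study to identify 26 individuals eligible for participation". Phase 3 of Study Procedures places allocation after that step: "Upon completion of the Screening/Consent and Initial Testing phases, participants will be randomized to one of two groups".

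Data Analysis & Statistical Considerations gives the size as follows: "the number of subjects randomized will be ~26 across the 1-year funding period with a target of 13 participants in each group". For Aim 2, the primary outcome is "Within-group differences in maintenance metrics and Senior Fitness test scores (THC group n=13 vs. SC group n=13" and the secondary outcome is "Between-group differences in maintenance metrics and Senior Fitness Test scores (13 vs. 13". The power statement sits in the primary outcome paragraph: "Using 80% power at alpha level 0.05, we should be able to detect an effect size around 0.62" and then "for analyses of pre-to-post change scores using steps per day as the primary outcome using paired t-tests".

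The analysis is by intention to treat, with significance at 0.05. The plan states no loss rate, no replacement rule and no method for missing outcomes. It does not say whether the test is one- or two-sided, nor which number of participants lies behind 0.62.

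**The concern.** The number randomised and the number attached to each analysis are the same, so the figures assume that everyone allocated supplies outcome data after about 3 months. For the Senior Fitness Test this means an in-person return visit by adults aged 60 or over with coronary heart disease. The move from 30 to 26 gives no protection, because it is complete before allocation.

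The power sentence has a second problem, and the two need to be handled together. The figure of 0.62 does not follow from 13 per arm in the first place. Correcting it at 13 alone would still describe full retention; allowing for loss without correcting 0.62 would start from a wrong baseline. The plan says that the pilot data will feed effect sizes and power for a later study, so whoever uses them needs to know what this sample could and could not detect.

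**Working it through.** **Inputs from the documents.** Up to 30 enrolled; about 26 randomised, 13 per arm; paired t-test within arm; alpha 0.05; power 80%; effect about 0.62.

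**Assumptions.** Two-sided test. Within-arm effects are in SDs of the change score; between-arm effects are in SDs of the outcome compared. Loss of 5% to 20%, because the documents give no rate.

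**Step 1: the plan's own figure.** Power of the paired t-test is P(T > t₀.₉₇₅,ₙ₋₁), where T is noncentral t with n − 1 degrees of freedom and noncentrality d√n.

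- n = 13, d = 0.62: noncentrality 0.62 × √13 = 2.24; critical value 2.18; power 54%.
- Solving for 80% power at n = 13 gives d = 0.85.
- A one-sided test at n = 13 gives 68% power at 0.62 and a detectable effect of 0.73.
- Pooling both arms (n = 26, two-sided) gives a detectable effect of 0.57 and 86% power at 0.62.
- A two-sample comparison of 13 with 13 has 33% power at 0.62.

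No variant using 13 or 26 reproduces 0.62. Two-sided, that effect needs 23 pairs (22 give 79%, 23 give 81%).

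**Step 2: where the margin goes.** 30 − 26 = 4 people, all before allocation. None is left for later loss.

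**Step 3: retention under assumed loss.** Expected number per arm is 13 × (1 − loss):

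- 5%: 12.4
- 10%: 11.7
- 15%: 11.05
- 20%: 10.4

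With independent losses, the chance that all 26 complete is 0.95²⁶ = 26%, 0.90²⁶ = 6% or 0.85²⁶ = 1.5%.

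**Step 4: detectable effects at the evaluable number.** These are for 80% power, two-sided 0.05. The between-arm figure uses noncentrality d√(n/2) with 2n − 2 degrees of freedom.

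| Evaluable per arm | Assumed loss | Within-arm (SD) | Between-arm (SD) | Within-arm power at 0.62 |
|---|---|---|---|---|
| 13 | none | 0.85 | 1.15 | 54% |
| 12 | about 10% | 0.89 | 1.20 | 50% |
| 11 | about 15% | 0.94 | 1.26 | 46% |
| 10 | about 20% | 1.00 | 1.32 | 42% |

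For a true within-arm effect of 0.85 SD, power falls from 80% at 13 to 72% at 11.

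**The case against.** **The counts do not contradict each other.** This stands. Thirty enrolled, 26 eligible and 13 + 13 allocated agree wherever they appear. Under intention to treat, 13 against 13 can fairly be read as the groups as randomised, and the text hedges with an approximate 26 and a target of 13. The gap is that a power figure is attached to those counts as if each person supplied an outcome. Intention to treat says which arm a person belongs to; without a missing-data method it does not supply a result for someone who does not return.

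**Loss may be small.** The plan excludes planned relocation and activity-limiting procedures, pays per completed visit, and offers remote coaching and questionnaires. A reader might infer that the trial will end with 11 per arm. The documents do not support that: 15% is an assumption, and at 5% about 12 per arm remain. A range is therefore right, and a single expected number is not.

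**The power sentence concerns steps per day, not the fitness visit.** This also stands. Steps come from a wearable and are averaged over 3 months, so a missed final visit need not remove them. The reduced numbers apply most directly to Senior Fitness Test change.

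**0.62 might already allow for loss.** It fits 22 to 23 pairs, close to 26 × 0.85 = 22.1 with both arms pooled. It would also fit 13 pairs if expressed in raw SD units with a pre-post correlation near 0.73 (an assumption). The documents say neither, and the pooled reading would not be a within-group figure.

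**It is a pilot.** This limits how much weight any power figure carries, but not the need for a stated figure to be correct.

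**Conclusion.** The power statement is wrong as written. With all 13 per arm retained, a two-sided within-arm paired t-test has about 54% power at 0.62, not 80%, and detects about 0.85 SD. Loss after randomisation, for which nothing is allowed, makes this worse: 46% power and 0.94 SD at 11 per arm. The larger part of the discrepancy is the 0.62 figure itself (0.62 to 0.85); an assumed 15% loss adds the smaller part (0.85 to 0.94).

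A reader might infer that full retention would restore the stated power. It would not: no one-sided, two-sided or two-sample calculation at 13 per arm gives 80% at 0.62. A reader might also infer that the 30-to-26 margin covers screen failures alone. Because allocation follows baseline testing, it also absorbs withdrawals between consent and randomisation.

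The conclusion rests on a two-sided test and an effect expressed in SDs of the change score. The size of the further drop depends on the assumed loss rate.

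**What to change.** In Data Analysis & Statistical Considerations, under Aim 2, make one combined edit:

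1. Label 13 per arm in the primary and secondary outcome lines as the number randomised.
2. Replace 0.62 with the within- and between-arm detectable effects tabulated above for 13, 12, 11 and 10 evaluable per arm. State 80% power, two-sided 0.05 and the SD in which each effect is expressed.
3. Mark the loss rates of about 10%, 15% and 20% as assumptions, and do not enter one of them as the expected number.
4. State that the reduced numbers apply most directly to Senior Fitness Test change, since steps per day may be available from partial wearable data.

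Enrolment and conduct stay as they are. Replacing the losses by recruitment would not fit the present cap in any case: 26 completers at 15% loss need 26 / 0.85 = 30.6, so 31 randomised, against a cap of 30 enrolled. The only cost is a less favourable stated figure. The edit does not settle how missing outcomes are handled under intention to treat, which the plan still leaves open.

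### One flat 0.05 level covers up to 24 Aim 2 tests, with no adjustment, order or exploratory label, so the chance of some false positive is well above 5%

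*Combined protocol and SAP*

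**What the plan says.** The only decision rule for Aim 2, under Data Analysis & Statistical Considerations, is "Data will be analyzed using Intent-to-Treat and statistical significance will be set at 0.05". The outcomes follow directly after it:

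- "Primary outcome: Within-group differences in maintenance metrics and Senior Fitness test scores (THC group n=13 vs. SC group n=13"
- "Secondary outcome: Between-group differences in maintenance metrics and Senior Fitness Test scores (13 vs. 13"

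The same section defines the maintenance metrics: "We will classify maintenance in two ways", namely mean steps/day and percent of prescribed steps/day. Study Procedures, Phase 2, lists the fitness battery: "chair stand test, arm curl test, chair sit and reach test, back scratch test, 8-foot up and go test, and step-in-place test". Phase 6 repeats it: "Follow-up testing includes the same tests completed during the initial testing phase, excluding the qualitative interview". A pre-to-post comparison is therefore possible for all six tests.

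The power sentence treats steps per day as the primary outcome, but the sentence labelled as the primary outcome also takes in the fitness scores. No composite fitness score is defined. No multiplicity adjustment, testing order or statement that any Aim 2 test is exploratory appears. The section describes the study as a pilot whose data will inform effect sizes and power for later work.

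**The concern.** With a threshold but no rule on which test it governs, any one of up to 24 comparisons can be reported as statistically significant at 0.05. Functional fitness is a named target of Aim 2, so a single chance result on one of six fitness tests could be presented as support for the aim. Naming one primary outcome would not settle this by itself, because the fitness tests would still each be open to a claim at 0.05 in both arms and between arms. If outcomes for the next study were picked because they crossed 0.05 here, with 13 per arm, their effect sizes would tend to be too large.

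**Working it through.** **The plan's own figures.** The documents state no familywise error rate, so there is none to reproduce. The power sentence uses the full 0.05 on one endpoint, which leaves no allowance for further tests. Its detectable effect of about 0.62 does not reproduce: a paired t-test with n=13 and 80% power detects 0.85 two-sided or 0.73 one-sided, and a pooled n=26 detects 0.57 or 0.50. That is a separate matter and does not enter the calculation below.

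**Number of tests.** There are 2 maintenance metrics and 6 fitness tests, so 8 endpoints.

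- Within arms: 8 × 2 = 16. Between arms: 8. Total: 24.
- Both maintenance metrics are averages over the intervention period. The monitor is dispensed at Initial Testing, and no baseline step count is described. If the metrics can only be compared between arms, the 2 × 2 = 4 within-arm tests drop out and 20 remain.
- Fitness tests alone: 6 × 2 + 6 = 18.

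**Expected false positives when nothing truly differs.** 24 × 0.05 = 1.2, or 20 × 0.05 = 1.0, whatever the correlation.

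**Chance of at least one, if tests were independent.** 1 − 0.95^k gives:

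- k = 8: 34%
- k = 16: 56%
- k = 24: 71%

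The last figure is too high, because the between-arm tests reuse the within-arm data.

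**Simulation.** This keeps that dependence. Settings: 13 per arm, 8 endpoints, two-sided t-tests at 0.05 (the plan does not state sidedness), no true change or difference anywhere, and 20,000 or more trials per setting. The correlation between endpoints is an assumption. Ranges in a cell cover repeat runs, with the two step metrics correlated either at the common value or at 0.8.

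| Tests counted | corr. 0 | 0.3 | 0.5 | 0.7 | 0.9 |
|---|---|---|---|---|---|
| All 24 | 63% | 56–58% | 49–51% | 40–41% | 26% |
| 20 (maintenance between arms only) | 57% | 52% | 46% | 37% | 25% |
| 16 within-arm | 56% | 50–52% | 44–46% | 36% | 23% |
| 8 between-arm | 34% | 29–30% | 25–26% | 20% | 12% |
| 18 fitness tests, within and between | 52% | 49% | 43% | 35% | 24% |
| Favourable fitness result only, THC arm or between arms | 22% | 19% | 17% | 14% | 9% |

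The last row counts only results that could be read as coaching improving fitness: six tests in the coaching arm and six between arms, in the favourable direction (0.025 each). Independence would give 1 − 0.975^12 = 26%; the shared data bring it down to 22%. Between arms alone it is 14% at zero correlation (1 − 0.975^6 = 14%), falling to about 5% at 0.9. Adding both step metrics to the last row raises it to at most 29%.

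**The case against.** The strongest reply is that a false claim for coaching is much less likely than the all-tests figure suggests. A significant change in the standard-care arm, or a significant worsening, cannot support such a claim, yet both count toward the 49–63%. This stands. A reader might infer that a false finding in favour of coaching is about as likely as not, and the documents do not support that. For fitness the figure is about 9–22%. It is still inflated: a single two-sided test gives a false favourable result 2.5% of the time.

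The correlations are also unknown. Six fitness tests taken by the same people could be strongly related, and at 0.9 the all-tests figure is 26%. This stands too, so the whole range has to be shown.

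The count of 24 is an upper figure, given the missing baseline for steps. However, the plan itself lists within-group differences in the maintenance metrics and a pre-to-post change in steps per day. With 20 tests the range is 25–57%, and the conclusion is the same.

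The plan is silent on adjustment; it does not say that tests are unadjusted or that each fitness test is analysed separately. Separate testing is an inference from the plural "scores" in the outcome sentences and the lack of a composite. It is a fair one, since nothing else is specified.

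Finally, this is a pilot meant to supply effect sizes, and estimates do that work whatever the p-values. That is a good reason not to require formal adjustment. It does not justify an open 0.05 rule: a plan confined to estimation would need no significance threshold, and this plan sets one.

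**Conclusion.** The point holds. As written, the plan allows up to 24 tests at 0.05 (20 if the maintenance metrics lack a baseline) with nothing limiting which may be claimed. With no true effect, at least one p<0.05 across all 24 is expected in about 49–63% of trials for correlations of 0.5 to 0, about 41% at 0.7 and 26% at 0.9. A falsely favourable fitness result for coaching is expected in about 17–22% for correlations of 0.5 to 0, falling to about 9% at 0.9. These figures rest on 13 per arm, two-sided tests, separate testing of the six fitness measures and assumed correlations. The plan should be amended, but the matter is one of wording and of what may be claimed. It does not affect the data or the estimates.

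**What to change.** Replace the significance sentence with text to this effect:

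*The 0.05 level applies to one pre-specified test: mean steps/day, in one named comparison. All other comparisons, including percent of prescribed steps, the six Senior Fitness Tests and all other within-arm changes, are exploratory and are reported as estimates with 95% CIs, without claims of statistical significance.*

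The sponsor must name the comparison. The between-arm one addresses Aim 2, and it can be computed even without baseline steps. The primary and secondary outcome sentences and the power statement would need to be brought into line with the choice.

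The cost is that no single fitness test or other within-arm change can be declared significant. Estimates and CIs do not change, and no visits or participants are added. If the between-arm test is named, the effect detectable with 80% power (two-sided, 13 per arm) is about 1.15 SD, against 0.85 for a within-arm paired test, and the plan should say so.

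Formal adjustment suits this study less well. Bonferroni over the 16 within-arm tests (0.05/16 = 0.0031) raises the detectable within-arm effect from 0.85 to about 1.29. Holm across the six fitness tests, run separately in each arm and between arms, with steps/day tested at 0.05 in all three comparisons, still leaves a familywise error of about 20–22% for correlations of 0 to 0.5.

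### Intent-to-Treat is stated without a definition or a missing-data method, and the only named test, run as written, omits any randomised participant without a follow-up Senior Fitness Test

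*Combined protocol and SAP*

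**What the plan says.** All of this is in the Combined protocol and SAP.

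- **Analysis set.** Data Analysis & Statistical Considerations, Aim 2: "Data will be analyzed using Intent-to-Treat". The term is not defined. No imputation, mixed model, carry-forward rule or sensitivity analysis appears anywhere.
- **Test.** The only inferential test named is in the power sentence of the Primary outcome paragraph, which refers to "pre-to-post change scores using steps per day as the primary outcome using paired t-tests". The primary outcome also covers Senior Fitness Test scores, but no other test is given for them. None is named for the secondary, between-group comparison.
- **Follow-up measurement.** Phase 6 – Follow-up Testing: "The repeated tests will be completed in one in-person visit". The Senior Fitness Test is one of those repeated tests.
- **Step metrics.** Both maintenance metrics are averages of device data over the 3-month intervention, so they do not depend on the follow-up visit.
- **Numbers.** The plan randomises about 26, targets 13 per group, and analyses 13 and 13. The margin from 30 enrolled to 26 (Design & Procedures) is for eligibility, not for loss after randomisation.

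**The concern.** A paired t-test needs two values per person. With no rule for a missing second value, the default in any software is to drop that person. For the Senior Fitness Test, one missed visit is enough.

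Three features of the plan make this matter:

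- Background & Significance says that activity after rehabilitation often falls back to sedentary habits. It is therefore plausible, though not shown, that those who miss follow-up are those who did worse.
- Contact differs by arm: six coaching sessions against one education session. Retention may differ too, and unequal loss would carry over into the between-group comparison.
- The stated use of the data is to develop effect sizes and power for a future study. A change estimated in those who returned, but labelled Intent-to-Treat, would pass straight into that calculation.

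**Working it through.** **Inputs.** From the plan: 13 per arm, 80% power, alpha 0.05, paired t-test, effect size about 0.62. Assumed, because the plan does not say: a two-sided test and 2 to 4 participants per arm without follow-up.

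**1. The plan's own figure.** Exact power for a paired t-test uses the noncentral t with df = n − 1 and noncentrality d√n. Solving for d at 80% power with n = 13 gives 0.85 two-sided or 0.73 one-sided. The stated 0.62 is not reproduced; power at 0.62 with n = 13 is 54% two-sided. That is a separate point. Here it means that the starting figure for the precision check is 0.85.

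**2. Precision lost if non-returners are dropped.** Same formula, two-sided:

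| n with both values | detectable d at 80% power | power at d = 0.62 |
|---|---|---|
| 13 | 0.85 | 54% |
| 12 | 0.89 | 50% |
| 11 | 0.94 | 46% |
| 10 | 1.00 | 42% |

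**3. Bias if non-returners differ.** Let the mean change in those who return be m, and let the k missing have a true mean change that is Δ worse. The mean for all 13 is [(13 − k)m + k(m − Δ)]/13 = m − kΔ/13, so the reported mean m is too favourable by kΔ/13:

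- k = 2: 2/13 = 15% of Δ
- k = 3: 3/13 = 23% of Δ
- k = 4: 4/13 = 31% of Δ

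This holds on the scale of any Senior Fitness Test item. For steps it applies only to participants with no usable step value. With an assumed Δ of 1,500 steps/day, a figure with no basis in the documents, it gives 231, 346 and 462 steps/day. These are illustrations only.

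**4. What a likelihood-based model would recover.** With baseline and follow-up as the two outcomes, the model's estimate of mean change is approximately

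(mean change in returners) + s × (baseline mean of all randomised − baseline mean of returners),

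where s is the slope of change on baseline among returners.

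- If loss depends on baseline only, this term removes the bias.
- If loss depends on the change itself, take equal variances at the two times and baseline-to-follow-up correlation ρ. Then s ≈ −(1 − ρ). If the returners' mean change is too high by B, their baseline mean is too low by about B/2. The term is about −(1 − ρ)B/2, so the share of bias removed is about (1 − ρ)/2. That is 15% at ρ = 0.7 and 10% at ρ = 0.8 (both ρ assumed). Simulation with roughly 20–27% missing gave 8–16%.

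The model therefore improves on the paired test but is not a full remedy, and the sensitivity analysis is needed.

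**5. The step metrics.** A participant who misses the visit or stops wearing the device early can still have a 3-month average. The difficulty is different: no rule says how much wear makes a valid average, so early weeks alone could stand for the whole period. Also, the monitor is dispensed at Initial Testing and the metrics cover only the intervention, so no pre-intervention steps/day value is defined for anyone.

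**The case against.** A reader might infer that the analysis is completers-only, or that the named test cannot deliver the named analysis set. The documents do not support either. They never say that participants without follow-up are excluded, and a paired t-test can be run on imputed data with all 13 in an arm. If Intent-to-Treat is meant only as analysis by assigned group, which the undefined term allows, there is a gap and not a contradiction. The paired t-test is also named only in the power sentence, for steps, and its use for the Senior Fitness Test is a reading of the Primary outcome paragraph. All of this stands, and it limits the point to what happens when the plan is run as written.

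Two further objections also stand in part. The step metrics do not depend on the follow-up visit, so a figure in steps/day does not measure the effect of missing it. And a likelihood-based model assumes data missing at random, which is not the loss most to be feared here; nor does it restore the information in unobserved follow-up values.

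It might finally be said that a mixed model is a matter of taste in a 26-person pilot. That carries less weight. Randomisation follows Initial Testing, so every randomised participant should have baseline fitness scores, and the plan offers no other way to keep them all in the analysis.

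**Conclusion.** The concern holds in limited form. Intent-to-Treat is stated but undefined, no missing-data method is given, and the one named test, used without imputation, leaves out any randomised participant who lacks a follow-up Senior Fitness Test. The sponsor should correct this; it does not invalidate the design.

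If 2 or 3 of 13 are lost in an arm, the detectable within-arm effect rises from 0.85 to 0.94 or 1.00, and the arm mean is too favourable by 15% or 23% of whatever difference exists between those lost and those who return. The number lost and the size and direction of that difference are assumptions. The detectable effects also assume a two-sided test. For steps, no bias figure can be attached to missing the visit.

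**What to change.** 1. **Define the analysis set**: all randomised participants, in the arm assigned.
2. **Senior Fitness Test.** For each score, replace the paired t-test with a likelihood-based model of baseline and follow-up in all randomised participants, with a common baseline mean, an arm-by-time term and small-sample (for example Kenward-Roger) degrees of freedom. Read the within-arm change and the between-arm difference, each with a 95% CI, from that one model.
3. **Steps.** Model weekly mean steps/day, with a simple prespecified covariance structure in view of the sample size, so that someone who stops wearing the device is not represented only by early weeks. Treat the percentage-of-prescribed metric the same way. Report arm means and the between-arm difference. Claim a within-arm change only if a pre-intervention step value is defined. Report how many participants have no usable step data, since they add nothing to this model.
4. **Sensitivity analysis.** Set missing follow-up values worse than baseline over a range stated in advance (a delta adjustment), in the unfavourable direction for each test. Do not set them to no change: in a maintenance trial that counts the missing as successes.
5. **Labelling.** Call any retained paired t-test a completer analysis, and give the number analysed in each arm.

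The cost is SAP wording and modest programming, with no new participants and no new data unless a baseline step period is added. The downside is the missing-at-random assumption, which step 4 tests but cannot remove.
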